7.6.3 Vital Signs

Vital sign parameters will be assessed after 5 minutes in supine position at the time points indicated in the Time and Events Schedule. The vital sign parameters that will be assessed are supine systolic blood pressure (SBP), diastolic blood pressure (DBP), heart rate, respiratory rate and body temperature.

Body temperature will be assessed using a thermometer preferably at approximately the same times of day for each measurement.

Any change from baseline in vital sign values occurring during the study that is considered to be clinically relevant by the Investigator should be recorded in the EDC system.

7.6.4 Electrocardiography

Single, 12-lead ECGs will be performed after a 5-minute rest at the time points indicated in the Time and Events Schedule. The ECG parameters assessed are heart rate, PR interval, QRS interval, QT interval. Values for QT corrected for heart rate (QTc) will be derived. QTc corrected according to Fridericia (QTcF) [6] will be the primary correction parameter. QTc parameters can be calculated subsequently if not immediately available at the site. If a subject has an elevated QTc >500 msec/min on assessment then repeat assessments in triplicate should be performed for confirmation.

Any change from baseline in ECG values occurring during the study that is considered to be clinically relevant by the Investigator should be recorded in the EDC system.

7.6.5 Physical Examination

A complete physical examination will be performed at the time points indicated in the Time and Events Schedule. A targeted physical exam may be performed at the Investigator's or his/her designee's discretion at the time points indicated in the Time and Events Schedule.

Physical examination at screening will include height and weight. To obtain the actual body weight, subjects must be weighed lightly clothed at screening. The height should be measured barefoot.

Any change in physical examination occurring during the study that is considered to be clinically relevant by the Investigator should be recorded in the EDC system.

7.7 TOTAL VOLUME OF BLOOD SAMPLING

The total volume of blood that will be drawn from each subject will be approximately 175 mL over the course of the study but no more than 25 mL per visit. In order to obtain additional information to ensure a subject's safety (i.e., an AE), additional blood samples (up to 50 mL) and/or urine samples may be taken at the discretion of the Investigator per standard of care.

7.8 APPROPRIATENESS OF MEASUREMENTS

The assessments that will be made in this study are standard, and are generally recognized as reliable, accurate, and relevant.

8. STUDY TERMINATION/COMPLETION

8.1 STUDY COMPLETION

A subject will be considered to have completed the study if he or she has completed the last follow-up visit (Day 100).

8.2 WITHDRAWAL OF SUBJECTS FROM STUDY

Subjects have the right to withdraw from the study at any time for any reason, including personal reasons. A subject can withdraw without giving a reason. The Investigator should, however, try to find out why a subject has withdrawn from the study and document the reason for withdrawal in the source documents and in the EDC system.

Subjects may withdraw from the study, or be withdrawn at the request of the Investigator or Sponsor (or designee). Each subject withdrawn from the study after receipt of any amount of study drug is to be encouraged to undergo as many post-study drug administration assessments as possible at the time of withdrawal. The reason for a subject's withdrawal should be recorded on the appropriate page(s) of the electronic Case Report Form. Reasons for withdrawal from the study may include, but are not limited to, the following:

- Withdrawal of consent;
- Significant subject noncompliance, defined as refusal or inability to adhere to the protocol requirements, e.g., subject restrictions and follow-up visit schedule;
- The Investigator determines that it is in the best interest of the subject to withdraw from study participation

If a subject is withdrawn from the study as a result of a product-related SAE (for details on AE reporting see Section 10), notify the Study Monitor and Sponsor within 24 hours. If a subject is withdrawn from the study due to an AE that is possibly related to study drug, notify the Sponsor within 2 days from the event.

If there is a medical reason for withdrawal, the Investigator will monitor the subject until satisfactory health has returned.

Subjects who terminate the study before completion of the scheduled study procedures for any reason (AE, withdrawal of consent, etc.) should be asked to complete study assessments (including safety) prior to withdrawal if possible. Subjects who withdraw for safety reasons should come for a safety follow-up visit within 14 days after discontinuation.

Study drugs assigned to a withdrawn subject must not be assigned to another subject.

8.3 STOPPING RULES OR DISCONTINUATION CRITERIA

The study will be overseen by a DSMB (see Section 5.6). Based upon any safety assessments and after mutual agreement with the Investigator (or designee) and the Sponsor, the study may be temporarily or permanently halted. Study enrollment and dosing will continue whilst the DSMB evaluates data.

Dosing will temporarily pause whilst the DSMB meets if:

- a drug-related or unexpected drug-related SAE occurs in at least 1 subject,

- 25% or more subjects have GI symptoms of Grade 3 following the first DSMB.

Doses may be adjusted downward at the discretion of the DSMB based on review of safety data including GI adverse events.

9. STATISTICAL METHODS

9.1 DETERMINATION OF SAMPLE SIZE

The study will enroll approximately 150 subjects. No formal sample size calculations were done for this study. The sample size is consistent with Phase 2a studies to assess safety and tolerability.

9.2 RANDOMIZATION AND BLINDING

This will be a double-blind study. The Contract Research Organization (CRO) and site study personnel and Visterra personnel will not be aware of which treatment (active study drug or placebo) the subjects have been given. Subjects will not be aware of which treatment they have been administered.

Subjects will be randomized 1:1:1 to receive VIS410 2000 mg, VIS410 4000 mg, or placebo. A randomization list with randomization numbers will be created. The randomization numbers must be used sequentially to ensure an overall balance; no randomization number can be skipped. Allocation of each subject to a given treatment sequence will be described in a randomization list prepared by Visterra or designee. The randomization will be balanced using randomly permuted blocks across the treatment groups.

The randomization list will not be available to the subjects, Investigators, (blinded) monitors, or employees of the clinical center involved in the management of the study before unblinding of the data, unless in case of emergency. The Sponsor's clinical team will also be blinded during the study as they will not have direct access to the randomization list. The CRO performing data management and statistical activities will receive a copy of the randomization list during database lock. Other team members will not have access to any data that could lead to unblinding.

Unblinding of the individual subject's treatment by the Investigator should be limited to medical emergencies or urgent clinical situations in which knowledge of the subject's study treatment is necessary for clinical management. In such cases, the Investigator must first attempt to contact the Medical Monitor or appropriate back up (contact information as detailed in a separate document), to discuss and agree to the need for unblinding to occur. The Medical Monitor or designee will answer calls 24 hours a day, 7 days a week, 365 days of the year. In situations in which the Investigator has tried, but is unable to reach the Medical Monitor, they should use their best judgment, based on the nature and urgency of the clinical situation, and may proceed with unblinding without having successfully reached and discussed the situation with the Medical Monitor.

Once a subject's treatment assignment has been unblinded, the Medical Monitor and study coordinator should be notified within 24 hours of unblinding of the treatment. Information relating to unblinding (e.g., reason and date) shall be clearly recorded in the subject's study file, as part of relevant standard operating procedures. In addition, the Investigator should consider whether the clinical event prompting unblinding should be considered an SAE, according to the regulatory definitions or criteria for SAEs, and if so, submit an SAE report to Visterra or designee.

Visterra or designee will also unblind any SAE reports that are serious, unexpected, and considered to be related to the study drug, in accordance with safety reporting guidance and regulations.

9.3 STATISTICAL ANALYSIS

VIS410 endpoints will compare aggregated VIS410 data as well as different dose levels of VIS410 to the placebo arm. Further details of the statistical methodology will be described in the statistical analysis plan (SAP).

9.3.1 *Analysis Populations*

The following analysis populations will be defined for the study:

Intent-to-Treat (ITT): All subjects randomized to treatment.

Modified Intent-to-Treat (mITT): All subjects who receive IV study drug and are confirmed influenza A positive by a molecular test at the central virological laboratory.

Safety Population: All ITT subjects who received IV study drug.

PK Population (PK): All subjects who received IV study drug with at least 1 PK parameter that can be calculated.

9.3.2 *Initial Characteristics of the Subject Sample*

Summary statistics will be provided per treatment group for demographic (e.g., age, height, weight, Body Mass Index, race, gender) and other initial subject characteristics (physical examination, medical history, concomitant diseases) will be provided per treatment group and for the total group. The ITT population will be used for the summaries.

Prior and concomitant medications will be coded using the World Health Organization Drug Dictionary.

9.3.3 *Pharmacokinetics*

Standard non-compartmental approaches using Phoenix WinNonlin (Pharsight Corporation, Princeton, NJ, USA; Version 6.3 or higher) will be used to estimate the PK parameters in serum and nasopharyngeal secretions (see Section 7.2.3) described below. All calculations will use the actual times recorded in the EDC system for dosing and sampling. Individual and mean (\pm SD) or median concentrations versus time profiles will be plotted by study period on both linear and logarithmic scales. Additional plots and PK parameters may be generated as appropriate. The PK population will be used for the summaries.

Serum Pharmacokinetics

Serum concentrations and the computed PK parameters will be listed by subjects for VIS410. Summary statistics of serum concentrations and PK parameters will be presented including means, geometric means, standard deviations, CV, medians and ranges, as appropriate.

Additional analyses and summaries may be generated as appropriate.

The following PK parameters will be determined for VIS410 in serum:

- C_{\max} : maximum observed serum concentration
- T_{\max} : time of C_{\max}
- $AUC_{0-\infty}$: area under the serum concentration-time curve from time 0 extrapolated to infinity
- $AUC_{0-\text{last}}$: area under the serum concentration-time curve from time 0 to the last measurable concentration
- $t_{1/2}$: terminal elimination half-life
- CL: total clearance
- V_d : volume of distribution

PK data from this study will be also analyzed by population PK modeling.

Nasopharyngeal Secretion Pharmacokinetics

Nasopharyngeal secretion concentrations and the computed PK parameters will be listed by subject for VIS410. Summary statistics of nasopharyngeal secretion concentrations and PK parameters will be presented including means, geometric means, standard deviations, CV, medians and ranges, as appropriate. Additional analyses and summaries may be generated as appropriate.

The following PK parameters will be determined for VIS410 from nasopharyngeal secretions:

- C_{\max} : maximum concentration observed from nasopharyngeal secretions
- T_{\max} : time of C_{\max}
- $AUC_{0-\infty}$: area under the nasopharyngeal secretion concentration-time curve from time 0 extrapolated to infinity
- $AUC_{0-\text{last}}$: area under the nasopharyngeal secretion concentration-time curve from time 0 to the last measurable concentration
- $t_{1/2}$: terminal elimination half-life
- Ratio of nasal:serum AUC

Additional PK parameters may be determined as appropriate.

9.3.4 *Viral Shedding*

Additional sensitivity analysis may be conducted excluding subjects that received concomitant antiviral therapy during the course of the study.

- One-way analysis of variance (ANOVA) (with treatment group as the factor) or other appropriate statistics detailed in the SAP to assess the difference between VIS410 treatment groups vs placebo in the area under the viral load-time curve (AUC) for influenza virus based on quantification of viral load from nasal swabs

- Descriptive statistics of the area under the viral load-time curve (AUC) for influenza virus based on quantification of viral load from nasopharyngeal swabs by treatment group.
- Descriptive statistics of the time to resolution of viral load and of the peak viral load by treatment group.

The mITT population will be used for the summaries.

9.3.5 *Signs and Symptoms of Influenza*

The difference between VIS410 and placebo will be assessed as outlined below.

- Frequency tabulation of the occurrence and severity of each of the subject-reported symptoms of influenza-like illness by assessment time point and by treatment group
- Descriptive statistics of the duration of each of the subject-reported symptoms of influenza-like illness by treatment group

Additional sensitivity analysis may be conducted excluding subjects that received concomitant antiviral therapy during the course of the study. The mITT population will be used for the summaries. Additional populations may be analyzed as described in the SAP.

9.3.6 *Immunology*

Immunological assessments will be summarized by parameter, treatment group, and time point using descriptive statistics:

- Anti-VIS410 antibody titers by ADA in serum
- Anti-influenza A antibodies by HAI in serum
- HAI levels to determine a proper immune response to the influenza infection

The mITT population will be used for the summaries. Additional populations may be analyzed as described in the SAP.

Anti-Drug Antibodies

Anti-VIS410 antibody titer will be summarized by treatment group and by time point using descriptive statistics.

9.3.7 *Exploratory Pharmacokinetic/Pharmacodynamic Analyses*

Various techniques will be used to explore exposure-response relationships, and to compare the strength of the relationship between each independent variable (e.g., AUC, C_{max} , and concentration at specific time point) and the dependent variables (e.g., viral AUC, peak viral load, and time to cessation of viral shedding, clinical symptoms, and additional endpoints). These techniques may include graphical and statistical methods, including the creation of boxplots, spaghetti plots, histograms, and a variety of linear, nonlinear, or logistic regression techniques and time-to-event methods. If appropriate, continuous independent variables will be evaluated as such, and as categorical variables (grouping subjects into exposure categories).

9.3.8 Safety

The ITT, and safety populations will be used for the safety summaries. Additional populations may be analyzed and this will be documented in the SAP.

Adverse Events

The original terms in the EDC system by Investigators to identify AEs other than symptoms of influenza A will be fully described and coded according to the Medical Dictionary for Regulatory Activities (MedDRA current version 19). The reported AEs will be allocated to phases based on their start date. All AEs will be listed. All AEs with onset during the treatment phase (TEAEs) will be summarized.

AEs will be summarized by treatment group and by MedDRA body organ system and preferred term, severity, relatedness, and seriousness. Classical symptoms of influenza including cough, sore throat, nasal congestion, fatigue, headache, myalgia or low-grade fever should not be reported as AEs unless there is a relationship between the event and study medication.

The difference in proportions of subjects with AEs, TEAEs, AESIs, and SAEs between treatment groups and their 95% CI will be calculated (primary safety endpoint).

Special attention will be paid to those subjects who died, discontinued the study drug due to an AE, or experienced a severe or serious AE. Summaries, listings, and narratives (also see Section 12.11) may be provided, as appropriate.

Injection Site Tolerability

Injection site tolerability is defined as AEs demonstrating significant injection site irritation or tissue damage. Injection site tolerability will be reported by variable, treatment group, and time point.

Complications of Influenza

Complications of influenza are defined as pneumonia, myocarditis, worsening of chronic bronchitis, other chronic pulmonary diseases, otitis, sinusitis, and death. Complications of influenza will be reported by variable, treatment group, and time point.

Clinical Laboratory Tests

Actual values and changes from baseline of each continuous biochemistry, hematology and urinalysis test will be evaluated using descriptive statistics by assessment time point and by treatment group. For categorical urinalysis tests, frequency tables of actual values will be provided by assessment time point and by treatment group.

Relative changes in clinical laboratory test values compared with values at baseline will be evaluated in according to the Division of Microbiology and Infectious Diseases (DMID) grading table or in accordance with the normal ranges of the clinical laboratory (below, within, or above normal range) for parameters for which no toxicity grades are defined. A shift from baseline table of abnormalities in clinical laboratory test parameters will be provided by assessment time point and by treatment group.

A listing of subjects with any clinical laboratory test result outside the reference ranges will be provided.

Vital Signs

Actual values and changes from baseline of heart rate, respiratory rate, temperature, SBP, and DBP measurements will be evaluated by means of descriptive statistics by assessment time point and by treatment group.

A shift from baseline table of vital sign abnormalities will be provided by assessment time point and by treatment group.

Electrocardiography

The ECG variables that will be analyzed are heart rate, PR interval, QRS interval, and QT interval. Values for QT corrected for heart rate (QTc) will be derived. QTc corrected according to Fridericia (QTcF) [6] will be the primary correction parameter.

Actual values and changes from baseline of ECG variables will be evaluated by means of descriptive statistics by assessment time point and by treatment group.

A shift from baseline table of ECG abnormalities will be provided by assessment time point and by treatment group. For absolute QTcF interval prolongation (>450, >480, >500 msec) and changes from baseline (increase >30 and >60 msec), a frequency table by assessment time point and by treatment group will be provided.

Physical Examination

Abnormal findings in physical examination will be listed.

9.4 INTERIM ANALYSIS

The following optional safety and efficacy interim analyses may be performed at the following times:

- After 75 subjects have completed the Day 28 visit
- After all enrolled subjects have completed the Day 14 visit

The optional interim analysis would review safety and efficacy results in a partially blinded fashion. If performed, the interim analyses will be included in the SAP and will be used to assist with the planning of future studies. The statistician performing the analysis and the PK/PD team at Visterra may be unblinded.

10. ADVERSE EVENT REPORTING

10.1 DEFINITIONS

Type of Event	Collection Period
AESIs ^a	28 days after drug administration
TEAEs	Entire study period ^b
SAEs ^c and Pregnancies	Entire study period ^{b, d}

^a If a subject was enrolled with a concurrent AESI, received investigational product, and then has worsening of an AESI (severity of symptoms), then this event should also be reported.

^b The entire study period is from the time a subject receives the study drug through the Day 100 Visit.

^c If the Investigator becomes aware of any related SAE after completion of the study, he or she is obligated to report this event.

^d If a subject or the female partner of a male subject, becomes pregnant during the study or within 100 days following study drug infusion, the Sponsor must be notified within 24 hours of the site's knowledge of the pregnancy; the subject or partner will be followed until the end of the pregnancy; and the infant will be followed for 1 year after the birth, provided informed consent is obtained.

Adverse Event

An AE is any untoward medical occurrence in a patient administered a medicinal (investigational or non-investigational) product in a clinical study. An AE does not necessarily have a causal relationship with the treatment. An AE can therefore be any unfavorable and unintended sign (including an abnormal finding), symptom, or disease temporally associated with the use of a medicinal (investigational or non-investigational) product, whether or not related to that medicinal (investigational or non-investigational) product.

This includes any occurrence that is new in onset or aggravated in severity or frequency from the baseline condition, or abnormal results of diagnostic procedures, including clinical laboratory test abnormalities.

New or worsening symptoms of influenza including cough, sore throat, nasal congestion, fatigue, headache, myalgia or low-grade fever should not be reported as AEs unless they result in an SAE (i.e., lead to hospitalization).

Adverse Event of Special Interest

An AESI (serious or non-serious) is one of scientific and medical concern specific to the Sponsor's product or program, for which ongoing monitoring and rapid communication by the Investigator to the Sponsor will be warranted. Such an event might warrant further investigation in order to characterize and understand it. Depending on the nature of the event, rapid communication by the trial Sponsor to other parties (e.g., regulators) might also be warranted (based on CIOMS VI).

For VIS410, the AESIs include the following:

- Abdominal cramping
- Diarrhea
- Nausea and vomiting
- Pruritus
- Rash

- Hypotension
- Throat tightening
- Trouble breathing or wheezing

Serious Adverse Event

An SAE is any untoward medical occurrence that at any dose meets any of the following conditions:

- results in death
- is life-threatening, i.e., the patient was at risk of death at the time of the event (e.g., ventricular fibrillation and anaphylaxis). The term does not refer to an event which hypothetically might have caused death if it were more severe.
- requires inpatient hospitalization or prolongation of existing inpatient hospitalization: Hospitalization refers to an overnight admission into hospital for the purpose of investigating and/or treating the AE. Hospitalization for an elective procedure, or routinely scheduled treatment for a pre-existing condition that has not worsened, is not an SAE.
- results in persistent or significant disability/incapacity, i.e., causing substantial disruption of the patient's ability to conduct normal life
- is a congenital anomaly/birth defect
- is medically significant, i.e., may not be immediately life-threatening or result in death or hospitalization but may jeopardize the patient's health or may require intervention to prevent one of the above outcomes. Examples of such events are intensive treatment in an emergency room or at home for allergic bronchospasm, blood dyscrasias, or convulsions that do not result in hospitalization or development of drug dependency or drug abuse.

Unlisted (Unexpected) Adverse Event

An AE is considered unlisted if the nature or severity is not consistent with the applicable product reference safety information (Investigator Brochure [5]).

Suspected Unexpected Serious Adverse Reactions

Suspected unexpected serious adverse reactions (SUSARs) are SAEs that are unexpected and judged by the Investigator or Sponsor to be related to the study treatment administered.

The Sponsor or designee will report SUSARs and other applicable SAEs to the appropriate regulatory authorities, Central Institutional Review Board (IRBs)/Ethics Committees (ECs) and Investigators as required, according to local law.

Treatment-Emergent Adverse Event

A TEAE is defined as any event not present prior to the initiation of the treatments or any event already present that worsens in either intensity or frequency following exposure to the treatments.

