The most common AEs observed were diarrhea (10/41, 24.4%) and headache (8/41, 19.5%). All diarrheal or loose stool AEs were observed in the VIS410-treated subjects and were usually mild to moderate, started ~2–4 hours after dosing, were transient and resolved spontaneously within 24 hours after dosing with no associated dehydration. The gastrointestinal (GI) events were dose proportional and the majority of the AEs were observed at the highest dose tested (50 mg/kg). None of the GI events were associated with a systemic allergic reaction or elevation in liver or biliary laboratory values. Mean hematology, serum chemistry, and urinalysis results were within the normal limits and the mean values and changes from baseline were similar across the treatment groups and placebo. Overall, mean vital sign measurements observed after dosing were similar to those observed at baseline. Mean changes from baseline were also similar across VIS410 dose levels, and no apparent treatment- or dose-related trends were observed.

The anti-drug antibody (ADA) data demonstrated a low level of positive ADA in 4 out of 30 subjects receiving VIS410 (Table 2). The subjects with positive ADA did not demonstrate any impact on their PK profile.

Table 2. Study VIS-C001 ADA Data

Cohort Dose (mg/kg)	No. of Confirmed ADA Positive	Pre-Infusion Titer	Confirmed Day	Positive Titer
2	0/6	None detected	NA	None detected
5	3/6	None detected	120	titer 10
		None detected	14	titer 10
		None detected	120	titer 40
		None detected	120	titer 40
15	1/6	None detected	120	titer 40
30	0/6	None detected	NA	None detected
50	0/6	None detected	NA	None detected

Phase 2a Challenge Study (VIS410-201). Study VIS410-201, “A Phase 2a Randomized, Double-blind, Placebo-controlled Study to Assess the Safety, Tolerability and Antiviral Activity of a Single Intravenous Dose of VIS410 in Healthy Subjects after a Viral Inoculation with Influenza A (H1N1),” was conducted at a single site in Antwerpen, Belgium by SGS Life Sciences. Briefly, 24 hours after inoculation with a 10^6 tissue culture infective dose (TCID) of naturally attenuated influenza A (H1N1) virus [7], subjects receive a single IV administration of VIS410 (2300 mg fixed dose, equivalent of 30 mg/kg) or placebo (7:5 randomization to VIS410:placebo). Subjects were quarantined 10 days post-inoculation and discharged thereafter.

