7.3 ILLNESS EVALUATIONS

7.3.1 *Viral Shedding*

Nasopharyngeal swabs to determine viral shedding will be taken as indicated in the Time and Events Schedule. Further details on sample collection, processing, shipment, and storage will be described in the laboratory manual.

7.3.2 *Signs and Symptoms of Influenza*

The FluPRO questionnaire will be completed by the subject at the time points indicated in the Time and Events Schedule.

Unsolicited (i.e., not collected via the FluPRO questionnaire) signs and symptoms will be collected and scored via a targeted physical exam that will be performed by the Investigator or designee. Timing of this assessment is provided in the Time and Events Schedule and is to be performed at the discretion of the Investigator or designee.

Body temperature will also be measured. Fever is defined as a body temperature $\geq 38^{\circ}\text{C}$.

The solicited and unsolicited signs and symptoms of influenza will not be reported as AEs as these constitute an endpoint of the study and will be recorded as such, unless a situation arises whereby it is the opinion of the Investigator to do so.

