7.6 SAFETY EVALUATIONS

The safety assessment in this study will be based on AEs, clinical laboratory tests, vital signs, and physical examination, as described in the following sections.

7.6.1 *Adverse Events*

AEs will be monitored continuously from signing of informed consent until the last study-related activity. At regular intervals during the study, subjects will be asked non-leading questions to determine the occurrence of any AEs. All AEs reported spontaneously during the course of the study will be recorded as well.

Subjects will be observed during infusion and for at least 2 hours after completion of administration of study treatment to allow monitoring for possible hypersensitivity reactions, anaphylactic reactions, or other AEs that occur during this time period.

All AEs will be recorded in the EDC system, except for the symptoms of influenza collected via the FluPRO questionnaire as discussed in Section 7.3.2.

For detailed definitions and reporting procedures of AEs, see Section 10.

7.6.2 *Clinical Laboratory Tests*

Blood samples will be collected by venipuncture or via indwelling cannula at the time points indicated in the Time and Events Schedule.

Standard laboratory tests will be performed by a central or local laboratory. Appendix 1 lists the biochemistry, hematology, coagulation, and serology tests that will be performed on the safety blood samples.

Creatine kinase-MB, creatinine kinase, and troponin are to be measured in the case where the subject has chest pain.

A midstream urine sample will be collected for urinalysis by dipstick, flow cytometry, and microscopic examination. Appendix 1 lists the urinalysis parameters that will be assessed.

Urine pregnancy tests will be performed at the time points indicated in the Time and Events Schedule.

The Investigator must review the laboratory report, document this review, and record any change occurring during the study he/she considers to be clinically relevant in the EDC system. Laboratory values outside the normal range will be flagged and their clinical relevance will be assessed by the Investigator.

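### Protocol 9.3.8 and 10.1 set contradictory exceptions for recording the same seven influenza symptoms as adverse events, so the primary AE and TEAE proportions depend on which section a site follows

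*Protocol*

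**What the plan says.** All the relevant sections share a default: symptoms of influenza are followed as an endpoint and are not entered as AEs. They differ on the exception.

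- Protocol 10.1, on new or worsening symptoms, excepts by seriousness: "headache, myalgia or low-grade fever should not be reported as AEs unless they result in an SAE (i.e., lead to hospitalization".
- Protocol 9.3.8, on classical symptoms, gives the same seven names and excepts by causality: "headache, myalgia or low-grade fever should not be reported as AEs unless there is a relationship between the event and study medication".
- Protocol 7.3.2 is broader in scope: "The solicited and unsolicited signs and symptoms of influenza will not be reported as AEs as these constitute an endpoint of the study". Its exception is discretionary: "unless a situation arises whereby it is the opinion of the Investigator to do so".
- Protocol 7.6.1 points both ways. For the exclusion it says: "All AEs will be recorded in the EDC system, except for the symptoms of influenza collected via the FluPRO questionnaire as discussed in Section 7.3.2". It then adds: "For detailed definitions and reporting procedures of AEs, see Section 10".

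The records produced under these rules feed the primary safety analysis in 9.3.8: "The difference in proportions of subjects with AEs, TEAEs, AESIs, and SAEs between treatment groups and their 95% CI will be calculated".

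**The concern.** Sections 9.3.8 and 10.1 cannot both be followed for a non-serious symptom that the Investigator attributes to study drug. An event left out at the site cannot be restored in the analysis. SAP 12.1 takes relatedness from the Investigator's recorded judgement, so it can only count what was entered.

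The situation will be common. Inclusion criterion 5 requires at least one moderate-to-severe symptom from nearly the same list, so every subject arrives with one, and sites will have to decide how to handle a change in it after the infusion. At stake are the any-AE and any-TEAE proportions. More directly exposed are the SAP 12.1 tables by preferred term, relationship and intensity, where each omitted event counts whether or not the subject had another AE.

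**Working it through.** **1. The rules applied to four cases.** Take a headache, which both lists name, and classify it by seriousness and by causality.

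| Headache | 7.3.2 | 9.3.8 | 10.1 |
|---|---|---|---|
| Non-serious, related | Discretionary | Reported | Not reported |
| Hospitalised, unrelated | Discretionary | Not reported | Reported |
| Non-serious, unrelated | Discretionary | Not reported | Not reported |
| Hospitalised, related | Discretionary | Reported | Reported |

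9.3.8 and 10.1 disagree in two of the four cases, in opposite directions. Neither exception contains the other, so they cannot be read as a general rule and its refinement. The second row is partly protected, because Protocol 10.7 separately requires every SAE to be reported whatever its suspected cause. The first row has no such protection.

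**2. Is there a tie-breaker?** No section ranks the rules. SAP 12.1 defines a TEAE by its start relative to the infusion and has no influenza-symptom rule. SAP 16.1 lists no change on this point.

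**3. Direction of the effect.** Let *a* and *b* be the true shares of subjects with a non-serious, related symptom from the list on VIS410 and on placebo. Let *f* be the share of subjects at sites that follow 10.1, with the remaining sites following 9.3.8. With *f* independent of arm and of the event, the recorded difference is (1 − *f*)*a* − (1 − *f*)*b* = (1 − *f*)(*a* − *b*). If *f* = 0, 0.5 or 1, then 100%, 50% or 0% of the true difference is recorded. The documents do not give *f*.

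**4. Scale for the any-AE proportion.** The plan states no figure to reproduce; Protocol 9.1 says no formal sample size calculation was done. About 150 subjects in three equal arms is 150/3 = 50 per arm, and 1/50 = 2.0 points. If a share *h* of an arm has such a symptom, and a share *p* has some other AE independently of it, moving from 9.3.8 everywhere to 10.1 everywhere lowers that arm's any-AE proportion by *h*(1 − *p*). Both inputs are assumptions.

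| *h* | *p* = 30% | *p* = 66.7% |
|---|---|---|
| 0% | 0 | 0 |
| 5% | 0.05 × 0.70 = 3.5 points | 0.05 × 0.333 = 1.7 points |
| 10% | 0.10 × 0.70 = 7.0 points | 0.10 × 0.333 = 3.3 points |

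For comparison, the approximate 95% half-width for a difference between two arms of 50 is at most 1.96 × √(2 × 0.5 × 0.5/50) = 0.196, or 19.6 points.

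**The case against.** **A drug-related headache is not a symptom of influenza.** On this reading 10.1 does not bar it. It falls under the general AE definition, and 10.6 requires it in the database. The reading is possible but not secure: 10.1 names headache with no causality qualifier, and 9.3.8 treats a related headache as an exception within the same list. Sites could reasonably differ.

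**Section 7.3.2 is permissive.** This stands. An Investigator who follows either 9.3.8 or 10.1 also complies with 7.3.2. The contradiction is between two sections, and 7.3.2 leaves it open. Nor does 7.6.1 send sites only to the narrow rule, since its exclusion cites 7.3.2.

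**FluPRO captures these symptoms anyway.** This stands in part. SAP 9.1.1 has daily data by arm to Day 10, and temperature is logged twice daily over the same days, so an early excess could still be seen. But those summaries use the mITT population, stop at Day 10 and carry no causality judgement, whereas TEAEs are collected to Day 100 and summarised in the Safety population.

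**Three stronger readings are tempting and not supported.**

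- With 150 subjects over 50 to 75 sites, or 2 to 3 per site, a reader might infer that recording habits will be unbalanced between arms. Subjects are individually randomised and the study is double-blind, so habits are independent of arm in expectation.
- A reader might size the effect from Phase 1: "The most common AEs observed were diarrhea (10/41, 24.4%) and headache (8/41, 19.5". Those were healthy volunteers, so an exclusion for influenza symptoms would not have applied to them. The figure also pools VIS410 with placebo and gives no relationship.
- FluPRO items 10, 15, 16, 31 and 32 overlap four AESI entries (breathing trouble, nausea and vomiting, abdominal cramping, diarrhea), so a reader might infer that AESIs are lost through 7.6.1. The seven named symptoms include no gastrointestinal or breathing term, and AESIs have their own list, 28-day collection period and eCRF event type. Under-recording is possible but not shown.

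**Conclusion.** The contradiction between 9.3.8 and 10.1 is real and unresolved, and it decides which events enter the primary safety proportions. Following 10.1 drops related non-serious events that 9.3.8 means to count and shrinks any true VIS410 excess in them toward zero. The consequence is attenuation and measurement noise.

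The size cannot be derived: no document gives the share of these symptoms that is both non-serious and related, or how sites divide between the rules. It could be zero. Under the assumed inputs above, the any-AE shift in one arm is 0 to 7.0 points, smaller than the uncertainty of a between-arm difference, so that proportion moves noticeably only if several subjects are affected. The relationship, preferred-term and intensity tables are more sensitive. Confidence is high on the textual conflict and low on its numerical effect. It should be fixed because the repair is cheap and an unrecorded event may not be recoverable.

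**What to change.** Reconcile Protocol 7.3.2, 7.6.1, 9.3.8 and 10.1 into one recording rule with one exception for the seven symptoms, worded identically in each place, and refer to it in SAP 12.1. Keep SAEs reportable in every case. If relationship is the criterion kept, tie it to the binary causality choice in 10.3. State in the same rule that AESI-list events are entered as AE/AESI even when FluPRO also captures them.

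The cost is a protocol clarification or amendment, a site reminder, and some duplicate capture between diary and AE pages. Some gastrointestinal symptoms caused by influenza would be counted as AEs in all arms. If enrollment has begun, events already left out may not be fully recoverable, and the study report should say so.
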